13.1 Evaluations During Treatment

13.1.1 Treatment Period

The treatment period consists of 6-7 weeks of concurrent RT and chemotherapy with BMX-001 followed by 1-2 weeks of BMX-001 (BMX-001 extends to week 8).

Physical examinations, vital signs (temperature, respiratory rate, blood pressure, and pulse), height (screening or baseline only), and weight must be performed at:

- screening
- baseline
- every week from weeks 1-8
- at each SOC visit after completing RT for a period of 1 year

More frequent examinations may be performed.

13.1.2 Physical Exam

A Physical Examination (PE) will include a general physical examination of major body systems, temperature, respiratory rate, blood pressure, heart rate, body weight, and height.

Height will be measured and documented at screening or baseline only.

13.1.3 Blood Pressure

In Phase 1 and the 6 subject safety lead-in in Phase 2, Blood pressure and heart rate will be measured pre-dose and then after 5 (\pm 1), 10 (\pm 1), 15 (\pm 2), 30 (\pm 5), 60 (\pm 5), and 120 (\pm 10) minutes on the loading dose. It will be checked pre-dose, 30 (\pm 5), and 60 (\pm 5) minutes all other days of BMX-001 administration.

For the Phase 2 study, blood pressure and heart rate will be measured pre-dose, 30 (\pm 5), 60 (\pm 5) and 120 (\pm 10) minutes on the loading dose. It will be checked pre-dose, 30 (\pm 5), and 60 (\pm 5) minutes post-dose on all other days of BMX-001.

Blood pressure should be measured with the following standardized techniques: patients should be seated in a chair; blood pressure measurement should begin after at least 5 minutes of rest; measurements should be taken preferably with a calibrated mercury sphygmomanometer.

13.1.4 ECG

ECG will be done for screening purposes and also prior to BMX-001 administration and at 60 (± 15) minutes after dosing on the loading day of BMX-001 and on a BMX-001 administration day during Week 1 and Week 4 pre-dose and at 60 (± 15) minutes after dosing. Results will be filed in the source for each subject.

13.1.5 Mucositis

Mucositis will be clinically assessed weekly during therapy and following therapy at clinic visits as listed in the table at the beginning of Section 13. Mucositis will be scored using the CTCAE version 4.03 and evaluation will also be done using the FACT-HN and the Oral Mucositis Weekly Questinaire-Head+Neck (OMWQ-HN) to be administered on screening and post therapy as listed in the table at the beginning of Section 13.

13.1.6 Xerostomia

Xerostomia will be assessed using the FACT-HN and the Xerostomia-Related Quality of Life Scale (XeQoLS) to be administered at baseline and post therapy as listed in the table at the beginning of Section 13.

Xerostomia will also be assessed by measurement of saliva production at baseline prior to BMX-001 administration and post therapy as listed in the table at the beginning of Section 13 using the following protocol:

Unstimulated: Clear mouth by spitting excess saliva into a disposable cup. Use a chewing motion to encourage saliva production and spit into a plastic cup for 3 minutes. The cup will be weighed after 3 minutes and compared to its tare weight to determine the volume of saliva produced.

Stimulated: Clear mouth by spitting excess saliva into a disposable cup. Use a 2x2" square of parafilm to chew on and stimulate saliva while spitting all produced saliva into a plastic cup

for 3 minutes. The cup will be weighed after 3 minutes and compared to its tare weight to determine the volume of saliva produced.

Due to institutional practices, subjects may be evaluated for Xerostomia by both the radiation oncologist and the medical oncologist. For consistency in reporting adverse events, whenever possible the clinical assessments of Xerostomia documented by the radiation oncologist will be entered into the CRF. When the subjects are seen by medical oncology only, the medical oncologist's clinical assessment will be used.

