syptoms from mucositis do not readily overlap with normalcy of diet, understandability of speech, and eating in public. Three levels of pain were assessed by a Likert scale which stated "I have pain" and had three response options: not at all/a little bit, somewhat, and quite a bit/very much. There was a significant difference in scores on the OMWQ-HN depending on this variable, F(2.62) = 38.6, p < .001, ES = .77-.99. There was also significant divergence between patients who used opioid analgesics compared to those who did not, such that those who were using analgesics scored worse (p = .002, ES = 0.87). Timepoints were 24-48 hours apart, providing a test-retest correlation of .89. Sensitivity to change was shown by determining changes in the pain item and normalcy of diet item to compare OMWQ-HN scores between no change/improved groups and worsened groups, t(63) = -4.3, p < .001, and t(63) = -2.6, p = .013, respectively. It has also been shown that the OMWQ-HN is more responsive than less symptom-focused QoL instruments in detecting early changes in symptoms related to oral mucositis [40].

The subjective impact of salivary gland dysfunction and xerostomia is assessed by collecting stimulated and unstimulated saliva production (See Section 13.1.6) and by using the Xerostomia-Related Quality of Life Scale (XeQoLS) developed at the University of Michigan (Appendix D). In its first form, the XeQoLS contained 8 questions developed through literature reviews, patient surveys, and the input of oncologists specializing in head and neck cancer, and was shown to parallel clinically measured salivary gland function [40-42]. Research showing that there were four domains to oral health-related quality of life led to the current 15 item scale that covers physical functioning (Cronbach's α = .85), personal/psychological functioning (α = .87), social functioning (α = .86), and pain/discomfort issues (α = .89). The Cronbach alpha coefficient for the total XeQoLS score was also significant (α = .96, p < 0.001) [43]. Internal validity was assessed by comparing the 15 item xeQoLS to the previous 8 item version (α = .36 to .73, p < 0.001). Correlations were significant between the scale and salivary flow (r =-.19 to -.28, p < .05) and there were expected between group differences when comparing those who had parotid-sparing radiotherapy compared to those that did not such that parotid-sparing provides better XeQoL [43].

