5.3 Phase 2 Objectives

 To confirm the safety and tolerability of the MTD of BMX-001 in conjunction with RT and concurrent cisplatin in a cohort of newly diagnosed patients with locally advanced head and neck cancers.

2) To further explore efficacy based on the impact of BMX-001 on mucositis, xerostomia, and radiation dermatitis in treatment of newly diagnosed patients with locally advanced head and neck cancers by evaluating the degree of these adverse events at 30-39 Gy, 40-49 Gy, 50-59 Gy, and 60-70 Gy, the duration of the adverse events, and evaluation of related patient-reported outcomes.

5.3.1 **Secondary Objective**

- 1) To assess the efficacy of BMX-001 at the MTD in a cohort of HNSCC patients based upon overall survival (OS), median progression free survival (PFS), and initial response to treatment.
- 2) To assess radiographic response in locally advanced HNSCC patients treated with standard RT and cisplatin with BMX-001 at the MTD.

5.3.2 **Exploratory Objectives**

3) To further describe patient-reported outcomes of HRQoL in locally advanced HNSCC with standard RT, cisplatin, and BMX-001 at the MTD.

6 Patient Selection

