DLQI											
Questionnaires											
FACT-HN		X								X	X
Questionnaire,											
PRO-CTCAE HN											
Assessment of	X										X
measurable											
disease by											
imaging ^f											
Toxicity	X	Ongoing						X			
Assessment											
BMX-001g, h		X	X	X	X	X	X	X	X	X	
Cisplatin i			X	X	X	X	X	X	Xi		
Radiation		Daily Monday-Friday for 6-7 weeks ^k									

^a Screening evaluation should be done within 21 days of starting BMX-001. The screening evaluation and baseline evaluation may be combined. Informed consent may be done within 28 days of starting BMX-001.

b Study assessments for History and Physical, medications, weight, vital signs, CBC w/ diff, CMP, and mucositis will be obtained at screening, baseline, weekly during therapy, and following therapy at clinic visits in which timing is scheduled under standard of care. Screening CBC with diff and CMP prior to the first dose of Cisplatin need not be repeated on week one for chemotherapy naïve subjects per institutional practice. Study visits following therapy (Week 9 and forward) will be under SOC and at minimum will include study data collection for the CRF at a post-therapy visit within 1 month of completion of

radiation (or within 1 month of completion of BMX-001 treatment) and at 6 and 12 months post radiation \pm 1 month. Mucositis will be scored using the CTCAE version 4.03. Toxicity assessment will continue to be obtained during year 1 to identify late toxicities possibly related to SOC or with study drug. PT/aPTT will be measured once and can be done at either screening or baseline.

- ^c Blood pressure and heart rate will be measured pre-dose and then after 30 (\pm 5), 60 (\pm 5), 120 (\pm 10) minutes on the loading dose. It will be checked pre-dose, and post-dose at 30 (\pm 5), and 60 (\pm 5) minutes all other days of BMX-001 administration.
- ^d Phase 2: ECG will be done at screening and will also be done pre-dose as well as at 60 (± 15) minutes after dosing on the loading day and on a maintenance dose injection day during week 1 and week 4, both pre and post dose at 60 (± 15) minutes.
- e Saliva production will be measured on baseline and the post-therapy measurement will be obtained at clinic visit within 1 month of the end of radiation therapy and at 6 and 12 months ± 1 month. If the post-therapy measurement cannot be obtained, this will not be considered a protocol deviation.

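### The saliva collection labelled unstimulated includes a chewing stimulus, so the trial takes no resting-flow measurement although it says that it does

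*Combined protocol and SAP*

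**What the plan says.** Section 4.5 says that salivary dysfunction is assessed by "collecting stimulated and unstimulated saliva production (See Section 13.1.6"), and the Section 13 schedule lists one saliva row covering both conditions. Section 13.1.6 gives the role: "Xerostomia will also be assessed by measurement of saliva production at baseline prior to BMX-001 administration and post therapy". Footnote e of the schedule sets the times at baseline, within 1 month of the end of radiotherapy, and at 6 and 12 months.

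The method is in Section 13.1.6. The first collection begins "Unstimulated: Clear mouth by spitting excess saliva into a disposable cup" and continues "Use a chewing motion to encourage saliva production and spit into a plastic cup for 3 minutes". The second gives the patient a "square of parafilm to chew on and stimulate saliva while spitting all produced saliva into a plastic cup", also for 3 minutes. Each cup is weighed against its tare weight. No other collection is described.

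Xerostomia appears in the second Phase 2 objective (Section 5.3): "To further explore efficacy based on the impact of BMX-001 on mucositis, xerostomia, and" radiation dermatitis. The listed xerostomia endpoint is the incidence of grade 2 or higher at months 1 and 6 (Sections 5.2 and 16.2.1).

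**The concern.** An unstimulated collection is meant to capture what the glands produce without a stimulus. This one includes a stimulus and states that its purpose is to raise output. The stimulus is of the same kind as in the paired test, so the two collections differ only in whether there is something to chew on.

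The label matters because the trial has no concurrent control (Section 4.3.2), and Sections 16.2.2.1 and 16.2.4 say that results will be set against historical controls. If the flow values were reported as unstimulated and placed beside a series collected at rest, the two would not measure the same thing. The instruction also sets no chewing rate or effort, so the strength of the stimulus may vary between patients and sites. Weighed saliva is the only instrument-based xerostomia measure in the plan. The others are questionnaires and clinical grading. A reading taken under the wrong condition cannot be converted to a resting value afterwards.

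**Working it through.** **Plan's own figure.** The plan gives no figure for saliva flow. Its only sample-size figure is the exact 95% interval width of 0.324 at n = 40 and proportion 0.50 (Section 16.2.4). With x = 20 and n = 40, the Clopper-Pearson limits are 0.3380 and 0.6620, a width of 0.3240. It reproduces, and this point does not change it.

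**Side by side (Section 13.1.6).**

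| | Labelled unstimulated | Labelled stimulated |
|---|---|---|
| Start | clear the mouth | clear the mouth |
| Action | chewing motion | chewing on parafilm |
| Stated purpose of the action | to encourage production | to stimulate saliva |
| Duration | 3 minutes | 3 minutes |
| Reading | weight minus tare | weight minus tare |

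The only difference is the parafilm. Neither column is a collection at rest, and no other section supplies or corrects one.

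**Extent.** At most 48 Phase 2 patients × 4 time points (baseline, about 1 month, 6 months, 12 months) = 192 readings carry the label.

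**Does this bias salivary preservation?** Take preservation as follow-up flow divided by baseline flow. The documents give no flow data, so the values below are assumptions chosen only to show the range. Let resting flow fall from 0.30 to 0.10 mL/min, so true preservation is 0.10/0.30 = 33%.

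- Chewing adds the same percentage at both times, for example 50%: 0.15/0.45 = 33%. No bias.
- Chewing adds 200% at baseline and 50% afterwards (damaged glands respond less): (0.10 × 1.5)/(0.30 × 3) = 0.15/0.90 = 17%. Preservation is understated.
- Chewing adds 50% at baseline and 200% afterwards: (0.10 × 3)/(0.30 × 1.5) = 0.30/0.45 = 67%. Preservation is overstated.

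The direction depends on how the response to chewing changes with gland damage, on which the documents are silent.

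**Absolute levels.** If chewing raises flow at all, each recorded value is above the resting value for that patient on that day. On the same assumption, 0.10 mL/min at rest yields 0.10 × 3 = 0.30 mL in 3 minutes. With an increment of 50% to 200% the cup holds 0.45 to 0.90 mL. This is where a comparison with resting-flow data fails.

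**The case against.** The strongest reply is that little in the plan depends on this measure. Flow is not a listed Phase 2 endpoint. The Phase 2 objective speaks of degree by dose band, duration and patient-reported outcomes. Section 16 contains no flow analysis. Section 13.1.6 names the questionnaires first and presents saliva as an additional assessment. All of this stands, and it limits how serious the point is.

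It is also fair to say that the same instruction applies before and after treatment, so change within a patient is measured by one method, and that chewing on nothing may be a weaker stimulus than parafilm. Both stand. Neither makes the collection a resting one. Someone might argue that the chewing motion serves only to gather saliva already in the mouth, but the instruction gives its purpose as encouraging production.

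A reader might infer more from two places, and the documents do not support it.

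- **That the result will flatter BMX-001.** This would need a known direction of bias in preservation, or a named historical series of resting flow. The working shows that the direction is open, and Section 16 names no series and specifies no flow comparison.
- **That the driest patients drop out unseen.** Footnote e says: "If the post-therapy measurement cannot be obtained, this will not be considered a protocol deviation". That does not say failures go unrecorded. Section 15.3 has missing data flagged to the investigator for a response. A patient who tries for 3 minutes and produces nothing already has a reading, a cup weight equal to tare, which is zero flow. Footnote e therefore gives no basis for a figure for overstated mean flow or for a rule that enters zeros.

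**Conclusion.** The point holds as an inconsistency between label and procedure. Section 13.1.6 does not measure what Section 4.5 and the Section 13 schedule say is measured, and the protocol's own wording is enough to show it. It affects every reading under the unstimulated label.

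Three things are lost: interpretation as resting flow, a clean contrast between the two collections, and valid comparison of absolute values with any historical unstimulated series. The primary endpoint, the graded xerostomia endpoint and the sample size are untouched. No size or direction of bias in preservation can be stated. The flows and increments in the working are illustrative assumptions, and the conclusion does not rest on them.

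**What to change.** For patients not yet at baseline, replace the instruction in Section 13.1.6 with a resting collection: after clearing the mouth, no chewing; let saliva pool and spit it into the cup for 3 minutes, before the parafilm test. Use this method for those patients at every time point.

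For patients whose baseline used the chewing motion, keep that method at follow-up so that their change from baseline stays comparable. Report their values as chewing motion without a bolus, not as unstimulated flow, and do not compare them with resting-flow historical data.

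The cost is one reworded instruction and a record of which method was used, with no added visit or procedure. The downside is two small sets for this measure. Section 11.10.4 reports that a subject in the BMX-HN-001 study, which appears to be this trial, had received the 28 mg loading dose by April 2019, so some baselines probably exist already. If the sponsor prefers not to split at most 48 patients, keep the present method for all and correct only the label, in Section 4.5, the Section 13 schedule, Section 13.1.6 and the report. Resting flow would then simply not be claimed.

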13.2 Re-treatment Criteria

Patients must not be experiencing a DLT in order to be retreated. Other dose modifications are specified in sections 10.5.1 (cisplatin) and 11.9 (BMX-001).

13.3 Follow-up Period

The follow-up period will consist of an approximately 24-month period following the end of RT treatment.

13.4 Early Withdrawal of Subject(s)

13.4.1 Criteria for Early Withdrawal

Subjects may voluntarily withdraw from the study at any time. The PI may also withdraw a subject from the study at any time based on his/her discretion. Reasons for PI-initiated withdrawal may include, but are not limited to the following:

- Adverse events
- Abnormal laboratory values
- Abnormal test procedure results
- Protocol deviation
- Administrative issues
- Disease progression
- Pregnancy

13.4.2 Follow-up Requirements for Early Withdrawal

Subjects who prematurely withdraw due to toxicity or progressive disease will be followed for six months after a subject is removed from the study. End of study requirements outlined above will be conducted. Subjects withdrawn for pregnancy will be followed until the pregnancy is ended.

13.5 End of Treatment

The end of treatment will occur when the patient comes off of study for the following reasons: completion of all study tests/procedures (approximately 24 months following completion of RT), progressive disease, unacceptable toxicity, allergic reaction to chemotherapy, allergic reactions to BMX-001, non-compliance with study follow-up, or withdrawal of consent. Patients will be followed for a minimum of 30 days after End of Treatment, and also followed for any unresolved adverse events considered related to study therapy. Patient death due to progressive disease will not be reported as a SAE.

13.6 End of Study

The study will be considered complete once enrollment has been met, follow-up procedures on all subjects have been conducted, and data analysis is concluded. The study may also be terminated early for any reason by the PI or sponsor. In order to terminate the study, all data extraction and analysis must be complete. Therefore, if any articles for publication are derived from the current study, they must be submitted and accepted with no further need for additional data review prior to termination with the IRB.

Subjects that are lost to follow-up will be documented in the patient record and in the study database. In the study database, the subject will be marked as "Patient Status Unknown," along with a corresponding explanation, if any. This status may also be documented on the "Off Study Form" in the study database.

13.6.1 Early Study Termination

This study can be terminated at any time for any reason by the PI or sponsor. If this occurs, all subjects on study should be notified as soon as possible. Additional procedures and/or follow up should occur in accordance with this protocol.

13.7 Outcomes Criteria

13.7.1 Time-to-Event Variables

Progression-free survival (PFS) is defined as the time between initiation of protocol treatment and the first recurrence of disease or death.

Overall survival will be defined as the time to death from the time of study enrollment.

13.7.2 Radiographic Response

Scans will be performed according to standard of care, which commonly would include screening or baseline, 3 months \pm 2 weeks from the end of radiation therapy, and then 12 months \pm 1 month from the end of radiation therapy. As part of this study protocol, the 12-month imaging (+/- 1-month post completion of radiation therapy or BMX-001 treatment) will be a chest x-ray that is required for research purposes.

The guidelines and criteria for radiographic response may be based on the RECIST 1.1 criteria and apply only to patients receiving definitive intent treatment:

- Complete Response: Disappearance of all enhancing tumor
- Partial Response: Greater than or equal to a 30% reduction in the size (sum of the largest perpendicular diameters) for all enhancing lesions taking as reference the baseline sum
- Progressive disease: At least a 20% increase in the size (sum of the largest perpendicular diameters) for all enhancing lesions, taking as reference the smallest sum recorded since the treatment started or the appearance of one or more new lesions
- Stable Disease: Evaluations that do not meet criteria for CR, PR or PD
- Not Assessable: Progression has not been documented and one or more sites have not been assessed.

If RECIST reads are not obtained per SOC per the institution, then imaging reads per the institutional standard of practice are acceptable.

Risks of the Chest X-Ray

Subjects will be exposed to radiation from the required chest X-ray. The amount of radiation from a chest X-ray is low — even lower than exposure through natural sources of radiation in the environment. The average dose of the chest x-ray is about 0.1 mSv (millisieverts) and the average annual effective dose of background radiation is about 3 mSv [61].

13.8 Quality of Life and Functional Assessments: HRQoL

The assessments of quality of life and function (XeQoLs, OMWQ-HN, DLQI, FACT-HN, and PRO-CTCAE HN) will be completed at the following time points: pre-treatment, end of treatment (during week 8) and at SOC visits following the end of therapy (this will include, at minimum, 1 month, 6 and 12 months \pm 1 month after treatment). Target windows for data collection will be: 1) for end of treatment should be collected within 1 month of the last day of radiation therapy; and 2) at 6 and 12 months should be collected within \pm 1 month of these time-points. However, if not possible, data should still be collected outside of these windows and analysis will account for the timing of data collection.

PRO-CTCAE HN: In addition to traditional physician obtained QoL parameters, we will incorporate a modification of the PRO-CTCAE which is a new outcome measure recently developed by the NCI designed to capture the patient's self-report of adverse events [60]. A subset of items drawn from the PRO-CTCAE system have been aggregated into a head and neck specific tool for use in this trial (PRO-CTCAE HN). The PRO-CTCAE HN measure tailored for use in this study consists of 25 items that evaluate the presence and/or severity of a range of symptoms, as well as the degree to which the symptom/toxicity interferes with usual function. Individuals respond to the questionnaire items using a 5-point Likert scale. PRO-CTCAE HN is designed to be completed by the patient without assistance from research staff similar to other quality of life measures.

All QoL/functional assessments listed below will be collected from patients at clinic visits via case report forms or by electronic data collection at the discretion of each clinical institution.

All quality of life questionnaires should be completed, even if the patient stops protocol treatment.

14 Safety Monitoring and Reporting

The PI is responsible for the identification and documentation of adverse events and serious adverse events, as defined below. PI will review and sign off on all adverse events and problems as they occur and will report them to the IRB in accordance with HRPP policies. At each study visit, the PI or designee must assess, through non-suggestive inquiries of the subject or evaluation of study assessments, whether an AE or SAE has occurred.

